5.6 Data Analysis

VETS data processing

The COP can be analyzed by transforming the time series into various traditional measures including sway area, sway velocity and AP and medio-lateral (ML) standard deviations. COP sway area is found using a principal component analysis, which approximates an ellipse around the x-y COP data using the first two eigenvectors. We will also assess COP velocity as a secondary dependent measure of balance dysfunction. COP velocity is calculated using the COP path length traveled in the x-y plane per time

epoch (0.01 sec). An instantaneous COP velocity is calculated for each sample and the average instantaneous COP velocity per trial. Multiscale entropy (MSE) is a nonlinear complexity measure of a time series over different temporal scales, which uses coarse-graining to average data points to generate a new time series ⁴¹. Repeating structure within the point-to-point fluctuations of the postural signals over a range of time series can be sensitive to sensory reweighting during upright standing ^{42, 43}. MSE quantifies the physiological noise due to the various integrating processes, such that control and coordination of muscular contractions patterns employed during balance control can be systematically evaluated ⁴⁴. Our primary measure will be COP sway area, but all measures will be analyzed particularly to compare and identify the most sensitive and selective measure.

Statistical Analyses

All statistical analyses will be performed using IBM SPSS Statistics Version 24 and MedCalc. For descriptive purposes, continuous data will be summarized with the number of non-missing values, mean, and standard deviation, minimum, median, and maximum and categorical data will be summarized with the number of non-missing values and the numbers (frequencies) of values equal to each of the possible categories, unless stated otherwise. Univariate analyses will examine data distributions, potential outliers and missing data. All statistical tests will be two-sided with a significance level of alpha=0.05. Unless otherwise stated, no multiplicity adjustment will be applied and no missing values will be imputed. For analysis of posturography data, each of the six VETS postural conditions (see Figure 2) will be tested three times for each participant from which an average is calculated for each condition. These within-subject, within-condition averages will be used in model building to assess between groups differences in balance (AIM 1a) and within-groups change in balance over time following surgical intervention (AIM 2).

For **AIM 1a**, mixed model ANOVA will be used to compare veteran group (CSM vs Control) and within-subject visual (EO, EC, and DYN) and surface conditions (FIRM and FOAM). Average COP sway, COP velocity, and MSE of COP sway velocity for each of the six VETS conditions will serve as dependent measures in separate models. Using Mauchly's tests, violations of sphericity will be detected, are corrected with Greenhouse-Geisser adjustments.

For **AIM 1b**, receiver operating characteristic (ROC) analyses will be conducted as a preliminary determination of sensitivity and specificity of VETS conditions to detect CSM. We will assess areas under the curve (AUC) and corresponding 95% confidence intervals, which will serve as indices of accuracy for CSM diagnosis. Using known groups (CSM and control veteran volunteers), we will compare AUC curves corresponding to 1) traditional diagnostic scale measures (e.g., mJOA scale, Nurick Scale, NDI, and SF-36), 2) VETS conditions, and 3) scale measures combined with VETS conditions. These analyses will serve as indicators for the degree the posturography, alone or in combination with scale measures, are sensitive and selective to CSM. An AUC = 0.50 will be considered chance level for correct classification into CSM and control groups. Differences in AUC for each of the three ROC curves will be accomplished using methods described by Delong et al ⁴⁵.

For **AIM 2**, VETS data for CSM veterans will be assessed for changes in balance following surgical intervention. VETS dependent measures outlined above will be entered into repeated-measures ANOVA with time point (pre-surgery, 2 weeks, 6 weeks, and 6 months post-surgery) entered as an additional repeated measure. Using Mauchly's tests, violations of sphericity will be detected, are corrected with Greenhouse-Geisser adjustments.

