5.0 Study Procedures

5.1 Study Design

For AIM 1, a cross-sectional design that includes within-subjects (VETS conditions) and between-subjects (veteran groups) factors will be used to compare balance and posture in patients awaiting surgery for CSM ($n = 20$) to a cohort of age and gender-matched non-CSM controls ($n = 20$). The 20 veterans with CSM recruited for AIM 1 will also serve as the sample for AIM 2, which is a longitudinal assessment of balance following surgical intervention for CSM. The data generated from the proposed study will provide a base estimate of the variance in our veteran groups for use in the power calculation for a larger follow up study

Veteran volunteers (CSM and control) meeting eligibility criteria will complete one session of VETS balance testing. Those veterans awaiting surgery for CSM will be asked to return for three additional sessions of VETS at designated time points scheduled 2 weeks, 6 weeks, and 6 months post-surgery. For returning CSM veterans, self-report measures will be collected at each additional time point to compare objective (VETS) and subjective (scale measures) assessments of functional impairment related to CSM following surgery. None of the procedures involved in this research project will alter standard of care associated with CSM or the surgical treatment. “Each patient will be cleared by one of the study doctors ([name], [name], or [name]) before participating in the post-surgery sessions. In the event that a patient is found to be physically incapable of safely participating in the first post-surgery session, they will not continue participation in the study until they are cleared by the study doctors. Thus, even if a patient is not cleared to participate in the two week post-surgery time point, they may be cleared to participate in the remaining two sessions (six weeks and six months post-surgery).”

Risks/Benefits of Participation

There are no risks associated with the questionnaires included in this study, as they ask only about physical symptoms and functioning associated with CSM. Although some emotional health questions will be included, they are not expected to be upsetting in any capacity.

The risks associated with VETS testing are minimal and are as follows:

- Discomfort from standing on the WBB or foam for a prolonged period of time
- Dizziness or disorientation when viewing the dynamic condition

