5.2 Recruitment Methods

Given the scope of the proposed study, a total sample size of 40 veterans is considered a realistic and achievable enrollment to generate pilot data. For AIM 1, a cross-sectional design that includes within-subjects (VETS conditions) and between-subjects (veteran groups) factors will be used to compare balance and posture in patients awaiting surgery for CSM ($n = 20$) to a cohort of age and gender-matched non-CSM controls ($n = 20$). The 20 veterans with CSM recruited for AIM 1 will also serve as the sample for AIM 2, which is a longitudinal assessment of balance following surgical intervention for CSM.

Drs. [name], [name] and [name] will identify potential participants for the CSM group by screening all CSM patients undergoing assessment and scheduling for surgical intervention. These potential participants will be referred to [name] study team, where a staff member will provide background information, additional pre-screening, and scheduling (if eligible and interested).

Healthy volunteers will be recruited using a poster/flyer within the SVAMC. Potentially interested participants will call the study staff, as prompted by the advertisement, and will undergo pre-screening and scheduling. A copy of this flyer may be found in the submission package. Healthy volunteers may also be recruited from the pool of participants who consented to future contact in the SMBI Data Repository. These individuals will be contacted by the research staff and will be asked if they are interested; the attached Telephone Script includes the language used for these participants.

For the cross-sectional arm of the study, veteran volunteers in the CSM and control conditions will be compensated \$40 for their participation. Veteran volunteers in the CSM group will have the opportunity to earn an additional \$40 for attending each of the three post-operative assessments, resulting in a maximum remuneration of \$160. Participants will be paid in full for all sessions attended, even if they cease participation before fully completing a session. Payment will be sent in the form of a VA check to the address specified by the participant.

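### Naming the most sensitive balance measure from the same 40 veterans, with no correction for the selection, overstates that measure's AUC: by about 0.03–0.06 if three measures compete, more if conditions compete too

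*Combined protocol and SAP*

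**What the plan says.** Section 5.6 (VETS data processing) sets a hierarchy: "Our primary measure will be COP sway area", with COP velocity as a secondary measure. The same sentence that names the primary then gives a second purpose: "all measures will be analyzed particularly to compare and identify the most sensitive and selective measure".

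Section 5.6 (Statistical Analyses) models sway, velocity and multiscale entropy (MSE) separately, each in six conditions. Its default is: "Unless otherwise stated, no multiplicity adjustment will be applied and no missing values will be imputed".

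For AIM 1b, the same section plans AUCs with 95% confidence intervals, "which will serve as indices of accuracy for CSM diagnosis". They are estimated in the enrolled CSM and control veterans. Three ROC curves (scales, VETS conditions, and both combined) are compared by DeLong's method, and the work is described as preliminary. Section 3.0 mentions composite balance measures under AIM 1B, but no section says which measure, condition or composite forms the VETS curve.

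The plan gives no selection criterion, candidate list, cross-validation, bootstrap correction or hold-out sample. Section 5.2 justifies the size by feasibility: "a total sample size of 40 veterans is considered a realistic and achievable enrollment to generate pilot data".

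**The concern.** The highest of several noisy AUCs tends to be high partly by chance. If the measure is chosen and its accuracy estimated in the same people, the winner's AUC is too high on average, even when every candidate is a single fixed score with a valid DeLong interval. DeLong's method, planned here for three curves, does not account for choosing a winner beforehand. At 20 per group the order of the measures is also unstable.

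At stake is the accuracy figure attached to whichever measure is called most sensitive. The AIM 1b VETS result is affected too if its condition or composite is settled after the AUCs have been seen. A sway-area AUC whose condition or composite was fixed beforehand does not carry this bias.

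**Working it through.** **Inputs from the plan.** 20 CSM and 20 controls (Sections 5.1 and 5.2; 20 + 20 = 40 agrees with the stated total). Three modelled measures in six conditions give 3 × 6 = 18 pairs (Section 5.6). The plan states no target AUC, power or expected optimism, so it has no figure of its own to reproduce beyond the total.

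**Assumptions not in the plan.** AUC is the criterion. Scores are binormal with equal correlation ρ of 0.3–0.8 between candidates. The groups are treated as independent, ignoring the age and sex matching.

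**Step 1: noise in one AUC.** Hanley–McNeil, with Q₁ = A/(2−A) and Q₂ = 2A²/(1+A):

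SE² = [A(1−A) + 19(Q₁−A²) + 19(Q₂−A²)] / 400

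- A = 0.75: (0.1875 + 0.7125 + 1.5268)/400 = 0.00607, so SE = 0.078 and the 95% half-width is 1.96 × 0.078 ≈ 0.15.
- A = 0.70: (0.2100 + 0.9208 + 1.6429)/400 = 0.00693, so SE = 0.083.

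A true gap of 0.05 between measures is small against this.

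**Step 2: bias by hand.** For k equally good candidates, the bias is roughly SE × √(1−ρ) × m, where m is the expected maximum of k independent standard normals (0.846 for k = 3, 1.820 for k = 18). This takes the correlation between AUCs to be about ρ. At true AUC 0.70:

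- k = 3: 0.083 × 0.837 × 0.846 = 0.059 (ρ = 0.3); 0.083 × 0.447 × 0.846 = 0.031 (ρ = 0.8).
- k = 18: 0.083 × 0.837 × 1.820 = 0.126 (ρ = 0.3); 0.083 × 0.447 × 1.820 = 0.068 (ρ = 0.8).

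**Step 3: bias by simulation** (4,000 studies per scenario, rank-based AUC, highest selected):

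| Candidates | True AUC of all | Mean AUC of winner, ρ = 0.3 / 0.5 / 0.8 | Bias |
|---|---|---|---|
| 3 | 0.70 | 0.76 / 0.75 / 0.73 | 0.03–0.06 |
| 18 | 0.70 | 0.823 / 0.810 / 0.773 | 0.07–0.12 |
| 18 | 0.50 | 0.641 / 0.622 / 0.581 | 0.08–0.14 |

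The simulation agrees with the hand calculation.

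**Step 4: stability of the ranking.** With three measures of true AUC 0.80, 0.75 and 0.70, the best ranks first in 66% / 69% / 83% of studies (ρ = 0.3 / 0.5 / 0.8); repeat runs gave 65–82%. The chosen measure's true AUC averages 0.779–0.791, so the mean loss against always choosing correctly is 0.80 − 0.791 = 0.009 to 0.80 − 0.779 = 0.021.

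**Step 5: does the correction work?** Bootstrap with the selection repeated in each resample (60 resamples, 500 simulated studies), all candidates truly 0.75:

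| k | ρ | Apparent | Corrected | Optimism left |
|---|---|---|---|---|
| 3 | 0.7 | 0.782 | 0.754 | 0.004 |
| 3 | 0.5 | 0.800 | 0.766 | 0.016 |
| 18 | 0.7 | 0.832 | 0.778 | 0.028 |
| 18 | 0.5 | 0.847 | 0.784 | 0.034 |

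Most of the bias goes. About 0.03 stays with 18 candidates.

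**The case against.** The strongest reply is that the plan already protects its main result. Sway area is primary, Hypotheses 1 and 3 are framed on sway area in the eyes-closed and foam conditions, and the search for a better measure is secondary work in a pilot whose ROC analysis is called preliminary. This largely stands between measures. It does not settle which of sway area's six conditions, or which composite, carries the VETS AUC, and a preliminary label does not remove bias from a reported AUC.

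Second, Section 5.6 names no criterion and does not promise to report a maximum AUC. That is correct. AUC is inferred because AIM 1b is the only sensitivity and specificity analysis.

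Third, the equal-AUC scenarios are unfavourable. Bias is near zero when one measure is clearly best and the measures are highly correlated. This also stands.

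A reader might infer more than the documents support:

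- *That 18 candidates compete.* Section 5.6 uses measure for sway area, velocity and MSE, and condition for the six tests. Three candidates is the plainer reading, and 18 is the upper case. Section 5.6 also lists AP and ML standard deviations, which could make five measures.
- *That the winner or its AUC passes into the follow-up study.* Section 5.1 carries forward only a variance estimate for that study's power calculation. No section lets a winner displace sway area.
- *That VETS gets many tries and each scale only one.* AIM 1b lists four instruments as examples, and Section 5.5 gives the SF-36 two component scores and eight scales. A one-sided tilt is not shown.
- *That the plan forbids a correction.* The multiplicity sentence is a default about adjustment; on optimism correction the plan is silent.

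**Conclusion.** The concern holds in limited form. Carrying out the stated purpose with the analyses as written would give the selected measure an AUC that is too high on average. The bias does not reach a sway-area AUC that is fully specified in advance. Its likely size on the plain reading is modest compared with the 95% half-width of about 0.15 on a single AUC, but it runs in one direction and the planned intervals do not reflect it. The ranking is unreliable when true AUCs differ by 0.05, yet a wrong pick costs little true accuracy. The overstated figure is therefore the main problem, more than the choice of measure. All sizes rest on AUC as the criterion and on the assumed true AUCs and correlations.

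**What to change.** Amend Section 5.6 as follows.

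1. Fix in advance the one sway-area condition or composite that carries the AIM 1b VETS AUC, whatever the other measures show. One built on the eyes-closed and foam conditions would match Hypotheses 1 and 3.
2. Label the comparison of measures exploratory. State the criterion and the full candidate list, and report every candidate with its paired AUC difference from sway area and 95% confidence interval.
3. If a best measure is named, report its bootstrap optimism-corrected AUC with the selection repeated in every resample, and the share of resamples in which it wins. Say that it needs confirmation in a new sample, because some optimism remains.

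The cost is a few sentences and a short bootstrap script, with no new visits or data. The downside is that the best-looking AUC becomes less favourable and the study will often be unable to name a winner. In simulation, the paired 95% interval excluded zero in the right direction in only 8–12% of studies for a true gap of 0.05, and 19–41% for a gap of 0.10.

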3.0 Objectives

AIM 1A: Determine whether and to what degree balance is altered in CSM. The degree of COP sway will be compared between CSM and controls in the six conditions comprising VETS testing.

Hypothesis 1: Impaired proprioceptive transmission in CSM will result in poorer balance (larger COP sway area) during EC conditions (eliminating the ability to compensate with visual feedback) and FOAM (reducing the reliability of somatosensory feedback) conditions compared to healthy veterans.

AIM 1B: Determine whether VETS enhances sensitivity and selectivity in the diagnosis of CSM. Composite measures of balance will be related to clinical assessment tools and their relationship with MRI.

Hypothesis 2: VETS will provide additional sensitivity and selectivity in identifying CSM compared to current clinical assessment tools.

Hypothesis 3: The degree of COP sway area during EC and FOAM conditions is expected to directly relate to the degree of spinal cord compression quantified from MRI, leading to a more sensitive gradation in the severity of CSM.

AIM 2: Evaluate the VETS scores after surgery for CSM. The degree of COP sway area under the 6 conditions will be compared before surgery, 2 weeks, 6 weeks, and 6 months after surgery.

Hypothesis 4: We expect surgery to reduce COP sway in EC conditions

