These risks will be minimized by allowing participants to step off the WBB/foam between trials if the participant indicates any sign of discomfort. If a participant feels unable to continue with the testing, they will be allowed to cease participation at any time. All participants will be advised to step off the balance board if they feel too dizzy, to minimize fall risk. Additionally, the experimenter overseeing the VETS testing will be trained to spot participants to guard against falls.

We do not expect the inclusion of patients with both CSM and an additional diagnosis (i.e. neuropathy or lumbar spine disease) to alter the risk profile for the study, as each patient will be screened by study clinicians before being allowed to participate in the study. Any patient who is not found physically capable of completing the study assessments will not be informed of the study.

Participants will receive no direct benefit as a result of participating in this study. However, developing the VETS assessment as an objective marker of balance dysfunction in CSM will benefit veterans in the future who are being diagnosed, treated, and rehabilitated for CSM.

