5.4 Inclusion/Exclusion Criteria

Inclusion criteria for the CSM group are:

- Symptoms of myelopathy in upper and lower extremities and stenosis of the cervical spine demonstrated by MRI or myelography
- Lower extremity muscle strength of 4 as quantified by manual muscle test (MMT) or above
- Ability to stand without support with eyes closed for 30 seconds or more.

Exclusion criteria for all study participants are:

- History of neurological disorder other than lumbar spine disease or peripheral neuropathy
- Inability to stand in an upright position with both feet together and eyes closed.

Veterans in the control group will be recruited via printed advertisement or through the SMBI Data Repository and age- and sex-matched with CSM veterans. Every effort will be made to ensure that the veteran participants enrolled in the proposed study are reflective of the VA population, with regard to sex and race/ethnicity. If any participant over the age of 89 happens to enroll, their exact age will be recorded as >89.

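### The AIM 1a model leaves out the matching variables, age and sex: the between-group sway comparisons forgo power if matching achieves balance and are biased if it does not

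*Combined protocol and SAP*

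**What the plan says.** - **Design.** Section 5.1 compares 20 veterans awaiting CSM surgery with "a cohort of age and gender-matched non-CSM controls", also 20. Section 5.4 likewise has controls "age- and sex-matched with CSM veterans". Neither these sections nor 5.2 gives an age tolerance, a pairing rule or a check of achieved balance.
- **Data.** The demographics form in Section 5.5 asks for age and sex.
- **Model.** Section 5.6 states for AIM 1a that "mixed model ANOVA will be used to compare veteran group (CSM vs Control) and within-subject visual (EO, EC, and DYN) and surface conditions". The two surfaces are FIRM and FOAM. Neither age, sex nor the matched set appears in any analysis. Tests are two-sided at 0.05.
- **Hypothesis.** Hypothesis 1 in Section 3.0 predicts "poorer balance (larger COP sway area) during EC conditions", and likewise in FOAM conditions, relative to healthy veterans.
- **Later use.** Section 5.1 adds that the data "will provide a base estimate of the variance in our veteran groups for use in the power calculation for a larger follow up study".
- **Comorbidity.** The exclusion criteria in Section 5.4 permit lumbar spine disease and peripheral neuropathy in all participants. Section 5.1 discusses them in CSM patients only as a matter of risk. No passage says that they are recorded as study data or analysed.

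**The concern.** Matching on a variable that predicts the outcome makes the two group means more alike by design, so the true variance of their difference falls. An error term without that variable still contains its variance, so the standard error is too large. The benefit of matching is paid for in recruitment and then not collected in the analysis.

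That reasoning needs the matching to have worked. Controls come from flyers and a data repository (Section 5.2). If they end up systematically younger than the CSM group, the same unadjusted comparison attributes part of an age effect to CSM.

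With 20 per group, precision on Hypothesis 1 is scarce. The variance carried into the follow-up power calculation also depends on whether age and sex are in the model.

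**Working it through.** **No figure to reproduce.** The plan gives no power, effect size or SD, and Section 5.2 justifies 40 participants by feasibility. From the documents: 20 vs 20, two-sided 0.05, six conditions. Everything else here is an assumption.

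**Assumptions.** Between-subject variance is 1, of which age and sex explain R² (a quarter of it through sex, with 15% of one sex). Noise variance within a condition is 0.5. Each control has the same sex as a CSM participant and an age within ±0.3 SD, centred on zero. The true difference is 0.8 of the total SD of each outcome.

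**Step 1: how far the standard error is off under balance.** Let V be the total variance of an outcome: 1 + 0.5 = 1.5 for one condition; 1 + 0.5/2 = 1.25 for the mean of the two EC conditions; 1 + 0.5/3 = 1.167 for the FOAM mean; 1 + 0.5/6 = 1.083 for all six. The unadjusted analysis uses V where V − R² applies, so the effective critical value is 2.024 × √(V/(V − R²)).

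EC mean, R² = 0.2: V/(V − R²) = 1.25/1.05 = 1.190; 2.024 × 1.091 = 2.209; actual two-sided level on 38 df about 3.3%. The simulation below gives 3.5%.

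**Step 2: simulated level and power** (20,000 replicates; unadjusted 38 df, adjusted for age and sex 36 df).

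| Comparison | R² | Unadjusted level, % | Power, unadjusted vs adjusted, % | Forgone, points |
|---|---|---|---|---|
| EC mean | 0 | 5.0 | 69.6 vs 69.5 | 0 |
| EC mean | 0.1 | 4.0 | 69.8 vs 72.7 | 2.9 |
| EC mean | 0.2 | 3.5 | 70.5 vs 76.1 | 5.6 |
| EC mean | 0.4 | 2.0 | 72.5 vs 84.6 | 12.1 |
| FOAM mean | 0.1 | 3.9 | 70.1 vs 73.2 | 3.1 |
| FOAM mean | 0.2 | 3.1 | 70.4 vs 76.6 | 6.2 |
| FOAM mean | 0.4 | 1.9 | 73.2 vs 86.0 | 12.8 |
| EC-FOAM alone | 0.1 | 4.3 | 69.6 vs 71.9 | 2.3 |
| EC-FOAM alone | 0.2 | 3.7 | 70.4 vs 75.1 | 4.7 |
| EC-FOAM alone | 0.4 | 2.5 | 72.0 vs 82.3 | 10.3 |
| Group main effect | 0.1 | 3.9 | 70.0 vs 73.5 | 3.5 |
| Group main effect | 0.2 | 3.1 | 70.7 vs 77.7 | 7.0 |
| Group main effect | 0.4 | 1.5 | 73.4 vs 87.1 | 13.7 |

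For the EC and FOAM means the adjusted level is 4.7-5.2% throughout. Under balance the mean null estimate is within 0.004 of zero. A separate simulation that took R² as a share of the total variance of one condition gave losses of 3.5, 7.3 and 15.0 points at R² 0.1, 0.2 and 0.4.

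**Step 3: if balance fails.** Suppose controls are 0.5 SD younger on average. The bias is 0.5 × √R² × √0.75, which is 0.14, 0.19 and 0.27 between-subject SD at R² 0.1, 0.2 and 0.4. The unadjusted EC-mean test then has a level of 5.6-7.6%. With age and sex in the model it is about 5-6%.

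**Step 4: interactions.** An age or sex effect that is equal in every condition cancels in EC minus EO (eyes open). The level of group-by-(EC minus EO) stays at 4.6-5.3%, with no power gain from adjustment. If the effects were twice as large in EC and FOAM conditions, it would be 4.5, 4.1 and 3.3%, and group-by-(FOAM minus FIRM) 3.8, 2.9 and 1.8%, at R² 0.1, 0.2 and 0.4.

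**Step 5: residual variance.** The unadjusted excess is V/(V − R²) − 1: 7, 15 and 36% for one condition, and 9, 19 and 47% for the EC mean.

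**Step 6: comorbidity (separate, and in the other direction).** Spurious difference = prevalence difference × shift in sway. At equal prevalence it is zero. At an assumed 20% vs 5% and 0.5 SD it is 0.15 × 0.5 = 0.075 SD (false-positive rate 5.6%). At 30% vs 5% and 1 SD it is 0.25 SD (11%).

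**The case against.** **This is a pilot sized by feasibility, with no power target.** A somewhat conservative comparison is then an efficiency choice, not an invalid analysis. That stands, and it limits the point to an improvement.

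**The plan names no EC, FOAM or single-condition contrast.** The team's illustrative analyses in Section 2.0 begin with the three-way interaction, which gains nothing from adjustment if age and sex act equally across conditions. This stands as a limit on scope. But those analyses go on to condition-specific group comparisons, and Hypothesis 1 is worded as a difference from healthy veterans within conditions, so the affected comparisons are the ones that answer it.

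**No R² is documented.** True, so the size of the loss is unknown. A reader might take the 12-13 points at R² = 0.4 as the expected loss, but it is the top of an assumed range.

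**A reader might infer that the tests are simply conservative and free of bias.** The documents do not support that. It rests on a close, zero-centred match, and no matching rule is given.

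**The follow-up variance.** If the follow-up study does not adjust, the unadjusted variance is the right input, and the documents do not say which analysis it will use. That stands, and it is why both should be reported.

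**Comorbidity.** A reader might infer that neuropathy and lumbar disease will go unrecorded, or that they confound the result. Neither is shown. Screening has to elicit them, the screening forms are not part of the text, and no prevalence or effect on sway is given. Nor does the word conservative extend to this issue.

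**Conclusion.** The omission is plain in the text, and the concern holds conditionally. To the extent that age and sex predict sway, the group main effect and the within-condition EC and FOAM comparisons are conservative if matching achieves balance, and biased if a systematic age or sex difference remains. Adjustment helps in both cases. Under the assumptions above, the power forgone at 0.8 SD is about 2-7 points at R² 0.1-0.2. At R² = 0.4 it is 10-13 points for the EC and FOAM comparisons and about 14 for the group main effect. At R² = 0 it is nil. Group-by-condition interactions are affected only if age or sex acts differently across conditions. The analysis as written is not invalid, but a nearly free improvement is available. Comorbidity is a separate and optional point.

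**What to change.** - **Model.** Add age and sex as covariates in the AIM 1a model, mean-centred so that the tests of visual condition and surface keep their meaning. Drop sex if all participants are of one sex.
- **Variance.** Report residual variance with and without the covariates, so that the follow-up power calculation uses the one that fits its analysis.
- **Cost.** SAP wording and two of 38 between-subject degrees of freedom. At R² = 0 the difference detectable with 80% power goes from 0.909 to 0.910 SD. No new measurement is needed.

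Separate and optional: record peripheral neuropathy and lumbar spine disease as yes/no, with the same questions in both groups, and tabulate them by group. Section 5.2 already has staff pre-screen the referred CSM patients, and healthy volunteers "will undergo pre-screening and scheduling", so this adds two fields to an existing step. Any analysis that excludes affected participants should be labelled exploratory. It can undo the matching, and it may change the CSM population studied, since Section 2.0 notes that impingement can occur at several spinal levels. It is also imprecise: if, say, 6 CSM and 2 control participants are excluded (14 vs 18), the 95% CI half-width, t × √(1/n₁ + 1/n₂), grows from 0.64 to 0.73 SD.
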